^bThe assessments from the last scheduled treatment visit of the previous double-blind trial will serve as the baseline measures for Trial 331-201-00195 for any assessment that is not new (unique) to the open-label trial. If a subject is unable to rollover immediately, up to 3 days may be permitted between the end of the double-blind trial and the start of IMP in the open-label extension trial; however, this must be discussed with the medical monitor (Note: assessments from the last scheduled treatment visit in the previous double-blind trial that are going to be used as the baseline measures for Trial 331-201-00195 will not need to be repeated if the subject enters Trial 331-201-00195 within 3 days).

^cWeek designations correspond to the end of the week (eg, Week 4 visit occurs at the end of week 4 of the trial).

^dTelephone contact will be made at Weeks 1, 6, and 10 to assess AEs and concomitant therapy.

^eIf a subject discontinues early, every effort should be made to complete the Week 12/ET evaluations as soon as possible and, whenever possible, prior to starting any new medication or treatment.

^fTelephone contact or clinic visit (investigator's discretion) for evaluation of safety, 21 days after the last dose.

^gNew (unique) assessments for Trial 331-201-00195 include informed consent, inclusion/exclusion criteria, confirmation of eligibility, changes in medical and psychiatric history, and dispensing of IMP.

^hAny post-screening/baseline visit should refer to screening/baseline when assessing change.

ⁱTo include measurement of waist circumference.

^jVital sign measurements include body weight, body temperature, systolic blood pressure, diastolic blood pressure, and heart rate. Blood pressure and heart rate will be measured in the following order: supine and standing after the subject has been in each position for at least 3 minutes. Vital signs scheduled for the same visit as blood samples are to be completed before blood is drawn.

^kSubjects should be fasting for a minimum of 8 hours prior to blood draws for screening/baseline laboratory assessments, if at all possible. If fasting blood samples are not feasible at screening/baseline, nonfasting blood samples may be obtained initially for determining eligibility for the trial and need to be repeated at the next visit at the discretion of the investigator.

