^lBlood samples for clinical laboratory tests should be drawn after a minimum 8-hour fast at Week 12/ET, if possible. Vital sign and ECG assessments should be completed before any blood samples are collected.

^mStandard ECGs will be performed after the subject has been supine and at rest for \geq 5 minutes prior to the ECG. Subjects will be enrolled in Trial 331-201-00195 based on the screening/baseline ECG results from the trial site. Any ECGs scheduled for the same visit as blood samples are to be completed before blood is drawn.

ⁿAll positive urine pregnancy test results must be confirmed by a serum test. Pregnancy tests can be performed at any point during the trial if pregnancy is suspected.

^oA urine drug screen and a blood alcohol test are required at the designated times, but either or both can be conducted at any time during the trial at the discretion of the investigator. See the exclusion criteria for exclusions based on urine drug screen and blood alcohol tests at screening/baseline.

^pThe "Since Last Visit" C-SSRS form will be completed at all visits for all subjects.

^qAdverse events recording will begin with the signing of the ICF for Trial 331-201-00195 and through the last scheduled trial visit (immediately reportable events will be collected through the last trial contact).

^rAll prescription and non-prescription therapy (pharmacological or other therapy) taken during the trial will be recorded. Details of prohibited therapies are provided in [Section 6.5.1](#).

^sSee [Section 6.1](#) for dose adjustment details.

^tSchedule an optional telephone call or other form of communication with the subject approximately 1 week (\pm 2 days) after the visit (eg, at Weeks 3, 5, 7, 9, and 11) to check on status.

2 Introduction

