8.8.2 Follow-up of Immediately Reportable Events

This trial requires that subjects be actively monitored for IREs up to 21 (± 3) days after the last dose of IMP is administered.

Immediately reportable events that are identified or ongoing at the last scheduled contact must be recorded as such on the AE page in eSource and the IRE form. If updated information (eg, resolved status) on IRE status becomes available after a subject's last scheduled contact (up to last in-clinic visit for the entire trial), this must be reported to the sponsor and recorded on the AE page in eSource and the IRE form, according to the appropriate reporting procedures described in [Section 8.8.3](#).

It is expected that the investigator will provide or arrange appropriate supportive care for the subject and will provide prompt updates on the subject's status to the sponsor. The investigator will follow IREs until the events are:

- resolved,
- stabilized,
- the subject is lost to follow-up, or
- has died.

Resolution means that the subject has returned to the baseline state of health and stabilized means that the investigator does not expect any further improvement or worsening of the subject's condition. The investigator will continue to report any significant follow-up information to the sponsor up to the point the event has resolved or stabilized, or the subject is lost to follow-up, or has died.

Refer to [Section 10.3](#) for additional information regarding the follow-up period for subjects that become pregnant or for pregnant partners of male subjects.

8.8.3 Follow-up and Reporting of Immediately Reportable Events Occurring After Last Scheduled Contact

Any new IREs reported to the investigator which occur after the last scheduled contact and are determined by the investigator to be reasonably associated with the use of the IMP, should be reported to the sponsor according to the procedures outlined in [Section 8.8.3](#). This may include IREs that are captured on follow-up telephone contact or at any other time point after the defined trial period and continue to report any significant follow-up information to the sponsor until the events are resolved or stabilized, or the subject is lost to follow-up or has died.

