Before trial enrollment, males and FOCBP must be advised of the importance of avoiding pregnancy during trial participation and the potential risk factors for an unintentional pregnancy. Subjects must sign the ICF confirming that the above-mentioned risk factors and the consequences were discussed.

A urine or serum pregnancy test for human chorionic gonadotropin will be performed at screening/baseline and at each check-in to the inpatient facility on all FOCBP. If a urine test is performed and is positive, the investigator will follow-up with a confirmatory serum test.

During the trial, all FOCBP should be instructed to contact the investigator immediately if they suspect they might be pregnant (eg, missed or late menstrual cycle). Male subjects must be instructed to contact the investigator immediately, during the trial, if their partner suspects that they might be pregnant (eg, missed or late menstrual cycle).

If a subject is suspected to be pregnant before she receives IMP, the IMP administration must be withheld until the results of serum pregnancy tests are available. If the pregnancy is confirmed, the subject must not receive the IMP and must not be enrolled in the trial. If pregnancy is suspected while the subject is taking IMP, the IMP must be withheld immediately (if reasonable, taking into consideration any potential withdrawal risks) until the result of the pregnancy test is known. If pregnancy is confirmed, the IMP will be permanently discontinued in an appropriate manner (eg, dose tapering if necessary for subject safety) and the subject will be withdrawn from the trial. Exceptions to trial discontinuation may be considered for life-threatening conditions only after consultations with the IRE contact (see the title page of this protocol for contact information).

The investigator must immediately notify the sponsor (within 24 hours) of any pregnancy associated with IMP exposure during the trial and for at least 30 days after the last dose of IMP, and record the event on the IRE form and forward it to the sponsor. The sponsor will forward the Pregnancy Surveillance Form(s) to the investigator for monitoring the outcome of the pregnancy.

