Due to COVID-19, delayed entry subjects are permitted to be screened for Trial 331-201-00195 up to 90 days after completing the last scheduled treatment visit of the previous double-blind BPD trial (discussion with the medical monitor is required if > 90 days have passed). These subjects will be screened for eligibility at a separate screening visit for Trial 331-201-00195, where they will undergo full assessments to determine eligibility. The screening period will be up to 21 days and may be extended upon discussion with the medical monitor. The delayed entry subjects will also undergo a separate baseline visit, and the assessments from that visit will serve as the baseline measures for Trial 331-201-00195. Delayed entry subjects will receive the first dose of IMP at the baseline visit.

Treatment Phase: Eligible subjects will receive daily treatment with open-label brexpiprazole beginning at the screening/baseline visit. Visits will occur at the end of Weeks 2, 4, 8, and 12. Telephone contact will be made at Weeks 1, 6, and 10 to assess adverse events (AEs) and concomitant therapy. In addition, an optional telephone call or other form of communication will be made with the subject approximately 1 week (\pm 2 days) after the visit (e.g., at Weeks 3, 5, 7, 9, and 11) to check on status. All subjects will receive up to 12 weeks of open-label treatment in this trial.

Follow-up: Subjects will be followed for safety via telephone contact or clinic visit 21 (\pm 3) days after the last dose of open-label brexpiprazole.

See [Figure 3.1-1](#) for a schematic of the trial design.

^aThe last visit of the previous double-blind BPD trial will serve as the baseline measures for Trial 331-201-00195. If a subject is unable to rollover immediately, up to 3 days may be permitted between the end of the double-blind trial and the start of IMP in the open-label extension trial; however, this must be discussed with the medical monitor.

^bTelephone contact or clinic visit.

^cTelephone contact will be made at Weeks 1, 6, and 10 to assess AEs and concomitant therapy.

Figure 3.1-1 Trial Design Schematic

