9.1 Adverse Events

All adverse events will be coded by System Organ Class (SOC) and Preferred Term (PT) according to the Medical Dictionary for Regulatory Activities (MedDRA). AEs that are sex-specific, e.g., ovarian cancer, will have their incidence rates evaluated for the specific sex.

Treatment-emergent AEs (TEAEs) are defined as AEs with an onset date on or after the first dose of IMP. In more detail, TEAEs are all adverse events which started after start of IMP; or if the event was continuous from baseline and was worsening, serious, study drug related, or resulted in death, discontinuation, interruption or reduction of study therapy. Adverse events occurring up to 30 days after the last day of IMP will be included in the summary tables.

The incidence of the following events in the open-label treatment phase will be tabulated by treatment group and overall using the Safety Sample:

- a) TEAEs
- b) TEAEs by severity
- c) TEAEs potentially causally related to the IMP
- d) TEAEs with an outcome of death
- e) Serious TEAEs
- f) TEAEs leading to discontinuations of the IMP
- g) AESI

The above summaries (b), (e) and (f) will also be prepared for TEAEs potentially causally related to the IMP.

In addition, incidence of TEAE during the open-label treatment phase of at least 5% by SOC and PT will be provided.

Incidence of TEAEs by SOC and PT will be summarized for sex, race, age and region subgroups.

Extrapyramidal symptoms (EPS)-related AEs will be grouped into five categories.

- 1) Dystonic Events, which include cervical spasm, dystonia, emprosthotonus, muscle contractions involuntary, muscle rigidity, muscle spasms, muscle spasticity, myotonia, nuchal rigidity, oculogyration, opisthotonus, pleurothotonus, risus sardonicus, torticollis, and trismus;
- 2) Parkinsonian Events, which include akinesia, asterixis, athetosis, bradykinesia, cogwheel rigidity, essential tremor, extrapyramidal disorder, freezing phenomenon, gait festinating, hypertonia, hypokinesia, hypokinesia neonatal, intention tremor, masked facies, parkinson's disease, parkinsonian crisis, parkinsonian gait, parkinsonian rest tremor, parkinsonism, tremor, and tremor neonatal;
- 3) Akathisia Events, which include akathisia, hyperkinesia, and psychomotor hyperactivity;

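### AE tables count events to day 30 after the last dose, but scheduled contact ends at day 18–24, so the last 6–12 days are only passively and selectively ascertained

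*SAP*

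**What the plan says.** **Counting rule.** SAP 9.1 defines treatment-emergent events as those starting on or after the first dose and then sets the outer limit: "Adverse events occurring up to 30 days after the last day of IMP will be included in the summary tables". The same section describes the incidence tables (all events, by severity, related, fatal, serious, leading to discontinuation, special interest) as covering the open-label treatment phase.

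**Scheduled contact.** The protocol has one post-treatment contact, by telephone or in clinic. Footnote f of Table 1.3-1 describes it as "for evaluation of safety, 21 days after the last dose", with a ± 3-day window in the column header. SAP 3.1 repeats the arrangement: "Subjects will be followed for safety via telephone contact or clinic visit 21" (± 3) days after the last dose. Neither document schedules a later contact.

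**Active monitoring.** Protocol 8.8.8.2 says: "This trial requires that subjects be actively monitored for IREs up to 21 (± 3) days after the last dose of IMP is administered".

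**After the last contact.** Protocol 8.8.8.3 covers new IREs that come to the investigator's notice, and asks for those that "occur after the last scheduled contact and are determined by the investigator to be reasonably associated with the use of the IMP".

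**End of AE recording.** Footnote q of Table 1.3-1 has recording run "through the last scheduled trial visit (immediately reportable events will be collected through the last trial contact"). The AE row of the same table nevertheless has a mark in the post-treatment follow-up column. Protocol 8.8.8.1 has non-serious events recorded whenever they are identified during the trial, and refers to those still ongoing at the last scheduled contact.

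**The concern.** The primary endpoint is the frequency and severity of AEs, so the period over which events are counted should match the period over which they are sought. Here the SAP's period is longer than the protocol's, and the SAP neither mentions nor explains the difference. SAP section 1 says that its methods prevail where analyses differ, but an analysis rule cannot create data that sites were not asked to collect.

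Three things follow:

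- A reader of the tables would take them to cover 30 days after dosing, when part of that window has no planned ascertainment.
- What does enter from the tail has been filtered on relatedness. SAP 9.1 tabulates related events, including related events by severity, related serious events and related events leading to discontinuation. For onsets in the tail, the relatedness result is largely set by the collection rule.
- Events starting after the last dose are pooled under a treatment-phase label, although the protocol separates a 12-week treatment period from a post-treatment follow-up period. None of the proposed AE tables (the CT-8 series) splits them.

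The route into the tables is also unclear. Protocol 8.8.8.2 sends IREs known at the last contact to both the AE page and the IRE form. For later events, 8.8.8.3 points only to 8.8.3, which stresses that the IRE form is not the AE page.

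**Working it through.** There is no plan figure to reproduce: the documents give no power calculation, expected event count or AE rate for this trial. The check is date arithmetic, then a comparison of passages.

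**Inputs**

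- Counting window after last dose: 30 days (SAP 9.1).
- Last scheduled contact and end of active IRE monitoring: 21 ± 3 days, so day 18 to day 24 (Protocol Table 1.3-1, 4.1 and 8.8.8.2; SAP 3.1).
- Treatment period for a completer: 12 weeks = 84 days (Protocol section 8).

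**Step 1. Length of the uncovered tail**

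Gap = 30 − day of last contact. Counting period for a completer = 84 + 30 = 114 days.

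| Last contact | Gap (days) | Share of 30-day window | Share of 114 days |
|---|---|---|---|
| Day 24 | 30 − 24 = 6 | 6/30 = 20% | 6/114 = 5.3% |
| Day 21 | 30 − 21 = 9 | 9/30 = 30% | 9/114 = 7.9% |
| Day 18 | 30 − 18 = 12 | 12/30 = 40% | 12/114 = 10.5% |

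**Step 2. What can enter the tables in each segment**

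| Segment | New non-serious AEs | New IREs |
|---|---|---|
| First dose to Week 12/ET | Sought at visits and calls | Sought at visits and calls |
| Week 12/ET to last contact | Sought at follow-up, per the AE row and 8.8.8.1; footnote q is unclear | Actively monitored |
| After last contact to day 30 | No route stated | Passive, and asked for only if judged reasonably associated with IMP |

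IREs include SAEs, AEs of special interest, potential serious hepatotoxicity and AEs from occupational exposure (Protocol 8.8.1), so the tail is not confined to serious events.

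**Step 3. Possible scale (illustration only)**

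The documents give no serious-event rate for this population. Assume a constant hazard and that a fraction r of subjects has a serious event over 84 days. The fraction with one in a gap of g days is 1 − (1 − r)^(g/84).

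- r = 1%, g = 6: 1 − 0.99^(6/84) = 0.07 per 100 subjects.
- r = 5%, g = 12: 1 − 0.95^(12/84) = 0.73 per 100 subjects.

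Across these assumed rates, fewer than one subject per 100 would have a serious event in the uncovered days.

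**Step 4. Footnote q against the rest of the protocol**

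- Footnote q distinguishes a last scheduled visit from a last contact and carries only IREs to the latter. Section 4.1 lists visits at Weeks 2, 4, 8 and 12, and the follow-up may be a telephone call.
- The AE row of Table 1.3-1 is marked at follow-up.
- Section 8.8.8.1 ties non-serious recording to the whole trial and to status at the last scheduled contact.
- Section 8 counts the follow-up as one of the trial's periods, and section 4.4 ends the trial on the post-treatment follow-up page.

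The last three items support collecting non-serious AEs through the follow-up contact. Footnote q is the outlier.

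**The case against.** The strongest reply is that a 30-day limit is an inclusion cut-off and not a promise of active follow-up. It says which recorded events to count. The tables give incidence per subject, so no person-time denominator assumes 30 complete days. All subjects share one follow-up schedule, so the gap does not by itself distort the split by parent-study treatment group; there is no concurrent control, and no hypothesis test is described for AEs. Counting known late events is the inclusive choice for safety, and deaths and serious events are listed individually (CT-9.1, CT-9.2). Most of this stands and is why the effect is rated small. It does not answer the relatedness filter in the tail, the treatment-phase label, or the disagreement over when recording ends.

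A reader might also infer four stronger claims that the documents do not support:

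- **That almost the whole 30 days is uncovered for non-serious AEs.** This needs footnote q to be read alone. The AE row, 8.8.8.1 and 4.4 point to collection through day 18–24.
- **That the tail holds only serious drug-related events.** Section 8.8.8.3 covers every class of IRE.
- **That the 30-day pregnancy duty in Protocol 10.3 is part of the same fault.** That duty concerns "any pregnancy associated with IMP exposure during the trial and for at least 30 days after the last dose of IMP". It is worded by exposure, without an investigator causality judgement, and does not promise a day-30 contact or test. A normal pregnancy is not an AE and goes on the AE page only with an abnormality or complication, so it barely touches these tables.
- **That the window should simply be cut at each subject's actual contact.** That would remove known late related events, possibly a death, from incidence, and would give subjects different cut-offs between day 18 and day 24.

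**Conclusion.** The point holds as a mismatch between counting and collection. The last 6 to 12 days of the 30-day window (20% to 40% of it, or about 5% to 11% of a completer's 114 days) have no scheduled ascertainment. The protocol provides there only for passively reported IREs judged reasonably associated with IMP. The likely effect on reported incidence is small. The selection on relatedness and the treatment-phase label are defects of presentation in the primary safety tables. Footnote q is a separate inconsistency within the protocol.

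The figures assume that the follow-up contact is made within its window. A missed contact lengthens the gap. The 5% to 11% share applies to a subject treated for the full 84 days; someone who stops early has the same gap over a shorter counting period, hence a larger share. The per-100 figures rest on assumed event rates and a constant hazard and show scale only.

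**What to change.** **SAP 9.1**

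- Report AEs with onset on treatment separately from AEs with onset after the last dose, and correct the open-label treatment phase label accordingly.
- Flag any event with onset after the last scheduled contact as passively ascertained, with a footnote saying that the protocol asks in that period only for IREs judged reasonably associated with IMP. Keep these events visible; do not drop them.
- State how an IRE reported after the last contact reaches the analysis database.

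**Protocol and SAP together**

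- Reconcile footnote q, the AE row of Table 1.3-1, sections 8.8.8.1 to 8.8.8.3 and the SAP's 30-day rule to one stated end of AE collection, saying explicitly what applies to non-serious events and what to IREs. The sponsor must choose the period.

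**Cost.** One extra split and a footnote in the AE tables, plus a wording clarification. The split and the flag need no new data beyond onset date, last-dose date and last-contact date.

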9.2 Clinical Laboratory Tests

Summary statistics for mean and mean change from baseline in the routine clinical laboratory measurements, prolactin concentrations, coagulation parameters (PT, aPTT, and INR), HbA1c, and TSH will be provided by parent study treatment group and by visit.

Potentially clinically relevant laboratory measurement test results in the open-label treatment period will be identified for the Safety Sample and will be summarized by parent study treatment group and listed. Criteria for identifying laboratory values of potential clinical relevance are provided in [Appendix 2](#).

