8.7.1 Clinical Laboratory Assessments

Clinical laboratory samples will be collected at the time points described in the schedule of assessments (Table 1.3-1) to perform the clinical laboratory assessments described in [Section 10.2](#). Refer to [Section 10.5](#) for criteria for identifying laboratory values of potential clinical relevance.

A central laboratory designated by the sponsor will be used for all laboratory testing (hematology [including HbA1c], serum chemistry [including prolactin], and urinalysis) required during the trial. The central laboratory should be used for all laboratory testing whenever possible (including unscheduled and follow-up, if needed). In cases where an immediate result is required for a particular laboratory test, the sample should be divided and sent to both a local laboratory and the designated central laboratory. Subjects should be fasting for a minimum of 8 hours prior to the blood draws, if possible. If fasting blood samples are not feasible at screening/baseline, nonfasting blood samples may be obtained initially for determining eligibility for the trial and need to be repeated at the next visit at the discretion of the investigator. Additional urine and blood samples may be collected for further evaluation of safety as warranted by the investigator's judgment. Reports from the central laboratory should be filed with the source documents for each subject. The central laboratory will provide laboratory results to the sponsor electronically.

Any value outside the normal range will be flagged for the attention of the investigator who must indicate whether or not a flagged value is of clinical significance. If one or more values are questionable, the test(s) may be repeated. If the result of any test (or repeat test, if done) is indicated as clinically significant in the samples taken at screening/baseline, the subject will NOT be enrolled into the trial without the permission of the medical monitor. In addition, unscheduled laboratory tests should be performed if clinically significant abnormalities are observed. Unscheduled laboratory tests may be repeated at any time at the discretion of the investigator for appropriate medical care.

Refer to Appendix 5 ([Section 10.5](#)) for criteria for identifying values of potential clinical relevance.

The total volume of blood to be collected during the trial will be documented in the ICF.

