7.1 Baseline Definition

Baseline is defined as the last available measurement prior to the first dose of open-label IMP in the open-label treatment phase.

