9.2.2 Metabolic Change

In addition to mean change from baseline, incidence of treatment emergent significant changes in fasting lipids, fasting glucose, and metabolic syndrome will be summarized by parent study treatment group using the following criteria.

Criteria for Treatment-Emergent Significant Change in Lipids and Glucose		
LAB PARAMETER	BASELINE ¹	ANYTIME POST BASELINE
LDL Direct, Fasting (MG/DL)	Borderline 100-<160	High ≥ 160
	Normal/Borderline <160	High ≥ 160
	Normal <100	Borderline/High ≥ 100
	Any Value	Increased ≥ 30
HDL Cholesterol, Fasting (MG/DL)	Normal ≥ 40	Low <40
	Any Value	Decreased ≥ 20
Triglycerides, Fasting (MG/DL)	Normal <150	High 200-<500
	Borderline 150-<200	High 200-<500
	Normal/Borderline <200	High 200-<500
	Normal <150	Borderline/High/Very High ≥ 150
	Any Value	Increased ≥ 50
Glucose Fasting, Serum (MG/DL)	Normal <100	High ≥ 126
	Impaired 100-<126	High ≥ 126
	Normal/Impaired <126	High ≥ 126
	Any Value	Increased ≥ 10

¹ BASELINE IS DEFINED AS THE LAST AVAILABLE MEASUREMENT PRIOR TO THE FIRST DOSE OF OPEN-LABEL IMP IN THE OPEN-LABEL TREATMENT PHASE.

Criteria for Treatment-Emergent Metabolic Syndrome	
DESCRIPTION	ANYTIME POST BASELINE ¹
Central Obesity	Waist Circumference $\geq 102\text{cm}(\text{MALE}), \geq 88\text{cm}(\text{FEMALE})$
Dyslipidemia	Triglycerides $\geq 150\text{mg/dl}$
Dyslipidemia	HDL $< 40\text{mg/dl}(\text{MALE}), < 50\text{mg/dl}(\text{FEMALE})$
Supine Blood Pressure	Systolic $\geq 130\text{mmHg}$ and Diastolic $\geq 85\text{mmHg}$

Criteria for Treatment-Emergent Metabolic Syndrome	
DESCRIPTION	ANYTIME POST BASELINE¹
Glucose Fasting, Serum	$\geq 100\text{mg/dl}$
Metabolic Syndrome	Met 3 Or More of the Above Criteria at a Visit

¹ BASELINE IS DEFINED AS THE LAST AVAILABLE MEASUREMENT PRIOR TO THE FIRST DOSE OF OPEN-LABEL IMP IN THE OPEN-LABEL TREATMENT PHASE.

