- CT-8.8.2 Listing of Serious TEAEs or Deaths that Are Related or Probably Related to COVID-19 (Safety Sample)
- CT-8.9 Incidence of Treatment-Emergent Adverse Events of Special Interests (AESIs) by System Organ Class and MedDRA Preferred Term (Safety Sample)
- CT-9.1 Listing of Deaths
- CT-9.2 Listing of Serious Adverse Events
- CT-9.3 Listing of Discontinuations Due to Adverse Events
- CT-10.1 Criteria for Laboratory Test Values with Potential Clinical Relevance
- CT-10.2.1 Listing of Laboratory Test Values with Potential Clinical Relevance by Subject (Safety Sample)
- CT-10.2.2 Listing of Laboratory Test Values with Potential Clinical Relevance by Test (Safety Sample)
- CT-10.2.3 Incidence of Laboratory Test Values with Potential Clinical Relevance (Safety Sample)
- CT-10.3.1 Mean Change from Baseline in Clinical Laboratory Test Results - Serum Chemistry (Safety Sample)
- CT-10.3.2 Mean Change from Baseline in Clinical Laboratory Test Results - Hematology (Safety Sample)
- CT-10.3.3 Mean Change from Baseline in Clinical Laboratory Test Results - Urinalysis (Safety Sample)
- CT-10.3.4 Mean Change from Baseline in Clinical Laboratory Test Results - Prolactin, by Sex (Safety Sample)
- CT-10.3.5 Mean Change from Baseline in Clinical Laboratory Test Results - Other Tests (Safety Sample)
- CT-10.4.1 Incidence of Laboratory Test Values with Potential Clinical Relevance - Prolactin (Safety Sample)
- CT-10.4.2 Listing of Laboratory Test Values with Potential Clinical Relevance - Prolactin (Safety Sample)
- CT-10.5.1.1 Incidence of Treatment-Emergent Significant Change in Lipids (Safety Sample)
- CT-10.5.1.2 Listing of Treatment-Emergent Significant Change in Lipids (Safety Sample)
- CT-10.5.2.1 Incidence of Treatment-Emergent Significant Change in Glucose (Safety Sample)
- CT-10.5.2.2 Listing of Treatment-Emergent Significant Change in Glucose (Safety Sample)
- CT-10.5.3.1 Incidence of Treatment-Emergent Metabolic Syndrome (Safety Sample)

- CT-10.5.3.2 Listing of Treatment-Emergent Metabolic Syndrome (Safety Sample)
- CT-10.6 Incidence of Potentially Liver Injury Related Laboratory Test Abnormalities (Safety Sample)
- CT-10.7 Listing of Potentially Liver Injury Related Laboratory Test Abnormalities (Safety Sample)
- CT-11.1 Criteria for Potentially Clinically Relevant Abnormalities in Vital Signs
 - CT-11.2.1 Listing of Potentially Clinically Relevant Abnormalities in Vital Signs (Safety Sample)

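### SAP 9.2 sets no fasting condition for mean change in glucose and lipids, and two metabolic-syndrome rows lack a fasting label, although the protocol does not guarantee fasting samples

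*SAP*

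**What the plan says.** **Sampling.** Protocol 8.7.1 sets the general rule: "Subjects should be fasting for a minimum of 8 hours prior to the blood draws, if possible". For screening/baseline, footnote k of Table 1.3-1 adds that "nonfasting blood samples may be obtained initially for determining eligibility for the trial", with a repeat at the next visit left to the investigator. For the last visit, footnote l says samples "should be drawn after a minimum 8-hour fast at Week 12/ET, if possible". Table 1.3-1 schedules laboratory tests only at these two points.

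**Baseline.** SAP 7.1: "Baseline is defined as the last available measurement prior to the first dose of open-label IMP in the open-label treatment phase". Fasting status plays no part.

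**Mean change.** SAP 9.2 plans "Summary statistics for mean and mean change from baseline in the routine clinical laboratory measurements", by parent-study treatment group and visit. Table CT-10.3.1 in the SAP's list of tables covers serum chemistry. According to Protocol Table 10.2-1, that panel holds glucose, triglycerides, and total, LDL and HDL cholesterol. Neither the text nor the table title mentions fasting.

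**Categorical results.** In SAP 9.2.2 every row of the lipid and glucose shift table is labelled fasting. In the metabolic-syndrome table the glucose row reads "Glucose Fasting, Serum", but the triglyceride row (150 mg/dL or more) and the HDL row carry no such label. SAP Appendix 2 applies its lipid limits, including the same 150 mg/dL for triglycerides, to fasting samples, and it gives separate glucose limits for fasting (100 mg/dL) and non-fasting (200 mg/dL).

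**The concern.** The SAP depends on fasting status in the shift table and Appendix 2, so the status has to be available in the data. It is then not used in the mean-change summaries or in two of the five syndrome components. Followed as written, the plan can subtract a post-meal baseline from a fasted Week 12 value, or the reverse, and can count a post-meal triglyceride towards metabolic syndrome.

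All subjects take open-label brexpiprazole, so change from baseline has no concurrent control to absorb a shift in fasting habits between visits. Laboratory change is a named secondary safety endpoint. At stake is whether a change of a few mg/dL in mean glucose or triglycerides can be read at all, and whether the syndrome table uses the same definitions as the rest of the SAP.

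**Working it through.** The plan states no figure on this point, and its sample size is not power-based, so there is nothing to reproduce. The check is a comparison of the texts followed by an illustration.

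**1. Can a non-fasting baseline be replaced?** For a direct rollover subject, the next clinic visit after screening/baseline is Week 2, after the first open-label dose. Under SAP 7.1 a repeat at that visit cannot become the baseline. Delayed-entry subjects (SAP 3.1) have separate screening and baseline visits, so a pre-dose fasting repeat is possible for them.

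**2. Where is fasting specified?**

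| Output | Fasting condition |
|---|---|
| Mean change, SAP 9.2 and CT-10.3.1 | none |
| Lipid and glucose shift table, SAP 9.2.2 | all rows |
| Metabolic syndrome: glucose | yes |
| Metabolic syndrome: triglycerides, HDL | none |
| Appendix 2 lipids | yes |
| Appendix 2 glucose | separate fasting and non-fasting limits |

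**3. Effect on mean change.** Let d be the meal effect, and f0 and f12 the non-fasting shares at baseline and Week 12. All three are assumed; none is in the documents.

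Spurious mean change = d × (f12 − f0).

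| Analyte | d (mg/dL) | f0 = 10%, f12 = 30% | f0 = 30%, f12 = 10% | equal shares |
|---|---|---|---|---|
| Triglycerides | 10 / 25 / 50 | +2 / +5 / +10 | −2 / −5 / −10 | 0 |
| Glucose | 5 / 10 / 20 | +1 / +2 / +4 | −1 / −2 / −4 | 0 |

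For example, 50 × (0.30 − 0.10) = +10 mg/dL.

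**4. Noise with equal shares f.** If fasting status is independent between visits, the SD added to an individual change is d × √(2f(1 − f)). For triglycerides this runs from 10 × √(2 × 0.1 × 0.9) = 4.2 to 50 × √(2 × 0.3 × 0.7) = 32.4 mg/dL. If the same subjects tend to be unfasted at both visits, it is smaller. For scale, the shift table flags an individual triglyceride rise of 50 mg/dL or more.

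**5. Triglyceride component.** Assume fasting triglycerides are lognormal with median 110 mg/dL and log-SD 0.5. The fasting rate at or above 150 is 1 − Φ(ln(150/110)/0.5) = 26.8%. A meal effect of 10 mg/dL raises the rate among unfasted samples to 31.5%, and one of 50 mg/dL raises it to 57.6%. Overall increase = f × (unfasted rate − 26.8%):

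- smallest: 0.10 × (31.5 − 26.8) = 0.5 percentage points
- largest: 0.30 × (57.6 − 26.8) = 9.2 percentage points

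**6. Metabolic syndrome.** The SAP requires three or more of five criteria at one visit. In a non-fasting draw, triglycerides may wrongly count, but the fasting-glucose criterion cannot be met. The two effects pull in opposite directions, so step 5 does not carry over to the syndrome rate.

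**The case against.** The strongest reply is that most of the problem is already handled. The shift table and the Appendix 2 lipid limits are fasting, Appendix 2 separates fasting from non-fasting glucose, and HbA1c is summarised. SAP 9.2.2 mentions mean change just before it names fasting lipids and fasting glucose, so a fasting mean change may be intended. CT-10.3.1 is only a title in a proposed list. The analyses are descriptive, and the primary endpoint is adverse events.

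This stands as a limit on reach: the gap is the mean-change summaries and two table rows. It does not close the gap, because no sentence or title makes the mean change fasting, and nothing explains why one syndrome row is labelled and the two lipid rows are not.

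Four stronger readings are tempting, and the documents do not support them:

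- *Mismatched pairs always bias the mean.* With equal shares at the two visits they cancel across subjects and leave only noise.
- *A true rise on brexpiprazole is understated.* That needs baseline to be the less fasted visit. The baseline rule is looser, but an early-termination visit is held as soon as possible and may also be unfasted. For subjects who received brexpiprazole in the parent trial, baseline is in any case already on drug.
- *The metabolic-syndrome count is inflated.* Step 6 shows it can move either way.
- *The protocol permits non-fasting samples at Week 12 as it does at baseline.* The acceptance is explicit only at baseline; at Week 12 the fast is requested without being mandatory.

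**Conclusion.** The concern holds within these limits. The SAP leaves fasting status out of mean change in glucose and lipids and out of two syndrome components, although the protocol does not secure fasting samples and the SAP uses fasting status elsewhere. The certain consequences are mixed pairs in the mean-change summaries wherever fasting status differs between visits, and a triglyceride criterion that a post-meal value can meet.

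Bias in mean change exists only if the non-fasting shares differ, and its sign is unknown. Under the assumed shares and meal effects it is 2 to 10 mg/dL for triglycerides and 1 to 4 mg/dL for glucose, in either direction. The triglyceride component could rise by 0.5 to 9.2 percentage points under the assumed distribution. These figures show scale and are not estimates for this trial. No meal effect was assumed for HDL, LDL or total cholesterol; the case for including them is consistency with the SAP's own fasting labels.

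This should be corrected before the tables are produced. It does not touch the primary endpoint.

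**What to change.** In SAP 9.2 and 9.2.2:

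1. Present mean change in glucose, triglycerides, total cholesterol, LDL and HDL for subjects with fasting samples at both baseline and post-baseline. Put all other pairs, including those of unknown fasting status, on a separate line.
2. Label the triglyceride and HDL rows of the metabolic-syndrome table as fasting.
3. State that samples with missing fasting status are treated as non-fasting.
4. State the syndrome denominator. Once three of the five components require fasting, a subject with a non-fasting draw has only 5 − 3 = 2 assessable components at that visit and cannot reach three. Such a subject should be shown as not evaluable, not as free of the syndrome.

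In the fasting-pair rows this makes the spurious term d × (f12 − f0) zero by construction. The cost is SAP wording and one filter on fasting status, with no change to trial conduct. The drawbacks are a smaller n in those rows and in the syndrome table, by an amount the documents do not allow one to compute, and possible selection of more compliant subjects. The separate line for other pairs keeps the excluded mean-change data visible.
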